9.5 Safety Analyses

9.5.1 Adverse Events

A solicited reporting system of AEs (serious and non-serious, related and not related) was used during this study, from the beginning of trabectedin + PLD treatment.

Whenever possible the investigator recorded the diagnosis, classified each adverse event in regards of seriousness and causal relationship to study drugs (trabectedin + PLD), and reported severity (grade).

AEs will be coded in the Medical Dictionary for Regulatory Activities (MedDRA) version 17.0 or higher by system organ class and a preferred term. Each event will be graded according to medical record documentation as 1 = mild, 2 = moderate, 3 = severe, 4 = disabling or life threatening consequences, and 5 = death.

The descriptive summaries presenting treatment emergent AEs will include AEs reported from Day 1 of study treatment to 30 days post last dose of study treatment. AE summaries will use the patient's maximum severity reported for each system organ class and preferred term. The corresponding summaries will be presented for AEs and SAEs grade 3 or higher.

Patient incidence of adverse drug reactions (ADR) related to trabectedin and related to PLD, respectively, will be tabulated by system organ class, preferred term and severity grade for all drug reactions and serious drug reactions. The corresponding summaries will be presented for ADRs and SADRs grade 3 or higher. ADR's relationship to treatment reported as unknown will be assumed to be related to both trabectedin and PLD.

In addition, and complementing the summaries above, AEs, SAEs, ADRs and SADRs will also be summarized by preferred term only, and in descending order of frequency.

A summary table will also be produced summarizing all event summaries and will include, AEs, SAEs, ADRs, SADRs, those leading to treatment discontinuation, and fatal events on study.

9.5.2 Concomitant Medication

The number and percentage of patients receiving each reported medication will be summarized as data is available.

9.5.3 Laboratory Test Results

Laboratory tests will be collected when available, at initiation of treatment and during the observation period. During the follow up period those laboratory tests associated with AEs and SAEs will be collected when available. Laboratory tests will be reported based on the treating clinician's usual practice procedures.

The number and percentage of patients with clinically significant results will be summarized.

9.5.4 Physical Examination

Physical examination data is collected at baseline and subsequent cycles, during the observation period.

Weight, height and BSA will be summarized, values at baseline, values and change from baseline to end of observation period (last dose of study treatment administration plus 30 days) will be presented. Additionally, the maximum and minimum observed post-baseline values will be summarized along with the change from baseline to the maximum and minimum observed value.

BSA may be summarized as reported by the investigator and as calculated from the weight and height data.

9.5.5 Exposure to Subsequent Surgery

The number and percentage of patients reporting subsequent surgery for ovarian cancer will be summarized along with the time from last dose of trabectedin to first post-surgery, the type of surgical procedure and anatomical site reported has been collected as free text which does not enable for statistical processing as data will not be coded for this study.

10. CHANGES FROM PROTOCOL-SPECIFIED ANALYSES

There are no significant changes to the protocol-specified analyses.

11. LIST OF PLANNED TABLES AND FIGURES

Table shells corresponding to this SAP will be documented separately. The shells document will contain the details regarding the content and layout of the tables and graphs to serve as requirement documentation for statistical programming.

Unless otherwise specified, the following outputs will be produced subject to study design and the availability of data, overall and by previous antiangiogenic usage.

11.1 Planned Tables

Category	Table Title
Disposition	Summary of Enrollment by Country and Site
Disposition	Reasons for Non-participation
Disposition	Summary of Inclusion and Exclusion Criteria
Disposition	Patient Disposition
Demographics and Baseline	Demographics and Baseline Characteristics
Demographics and Baseline	Medical History
Demographics and Baseline	Prior Anticancer Therapy
Demographics and Baseline	Baseline Imaging
Effectiveness - Primary Endpoint	Progression-free Survival
Effectiveness - Secondary Endpoint	Best Tumor Response
Effectiveness - Secondary Endpoint	Overall Survival
Effectiveness	Summary of Symptomatic Response
Other Secondary Endpoints	Summary of ECOG Performance Status
Treatments - Secondary Endpoints	Exposure to Trabectedin
Treatments - Secondary Endpoints	Trabectedin Dose Modification
Treatments - Secondary Endpoints	Exposure to PLD
Treatments - Secondary Endpoints	PLD Dose Modification
Treatments - Secondary Endpoints	Subsequent Anticancer Therapy after Stopping Trabectedin
Safety	Overall Summary of Patient Incidence of Treatment-Emergent Adverse Events
Safety	Overall Summary of Patient Incidence of

Category	Table Title
	Treatment-Emergent Adverse Drug Reactions
Safety	Treatment-Emergent Adverse Events
Safety	Treatment-Emergent Adverse Drug Reactions Related to Trabectedin
Safety	Treatment-Emergent Adverse Drug Reactions Related to PLD
Safety	Treatment-Emergent Serious Adverse Events
Safety	Treatment-Emergent Serious Adverse Drug Reactions Related to Trabectedin
Safety	Treatment-Emergent Serious Adverse Drug Reactions Related to PLD
Safety	Treatment-Emergent Adverse Events Grade 3 or Higher
Safety	Treatment-Emergent Grade 3 or Higher Adverse Drug Reactions Related to Trabectedin
Safety	Treatment-Emergent Grade 3 or Higher Adverse Drug Reactions Related to PLD
Safety	Treatment-Emergent Serious Adverse Events Grade 3 or Higher
Safety	Treatment-Emergent Grade 3 or Higher Serious Adverse Drug Reactions Related to Trabectedin
Safety	Treatment-Emergent Grade 3 or Higher Serious Adverse Drug Reactions Related to PLD
Safety	Treatment-Emergent Adverse Events in Descending Order of Frequency
Safety	Treatment-Emergent Adverse Drug Reactions Related to Trabectedin in Descending Order of

Category	Table Title
	Frequency
Safety	Treatment-Emergent Adverse Drug Reactions Related to PLD in Descending Order of Frequency
Safety	Treatment-Emergent Serious Adverse Events in Descending Order of Frequency
Safety	Treatment-Emergent Serious Adverse Drug Reactions Related to Trabectedin in Descending Order of Frequency
Safety	Treatment-Emergent Serious Adverse Drug Reactions Related to PLD in Descending Order of Frequency
Safety	Treatment-Emergent Grade 3 or Higher Adverse Events in Descending Order of Frequency
Safety	Treatment-Emergent Grade 3 or Higher Adverse Drug Reactions Related to Trabectedin in Descending Order of Frequency
Safety	Treatment-Emergent Grade 3 or Higher Adverse Drug Reactions Related to PLD in Descending Order of Frequency
Safety	Treatment-Emergent Grade 3 or Higher Serious Adverse Events in Descending Order of Frequency
Safety	Treatment-Emergent Grade 3 or Higher Serious Adverse Drug Reactions Related to Trabectedin in Descending Order of Frequency
Safety	Treatment-Emergent Grade 3 or Higher Serious Adverse Drug Reactions Related to PLD in Descending Order of Frequency
Safety – Conmeds	Concomitant Medications

Category	Table Title
Safety – Labs	Summary of Hemoglobin
Safety – Labs	Summary of Absolute Neutrophil Count (ANC)
Safety – Labs	Summary of Platelet Count
Safety – Labs	Summary of Serum Creatinine
Safety – Labs	Summary of Total Bilirubin
Safety – Labs	Summary of Total Alkaline Phosphatase
Safety – Labs	Summary of Aspartate Aminotransferase (AST)
Safety – Labs	Summary of Alanine Aminotransferase (ALT)
Safety – Labs	Summary of Creatine Phosphokinase (CPK)
Safety – Labs	Summary of Albumin
Safety – Labs	Clinically Significant Laboratory Tests
Safety – Physical Examination	Physical Examination – Weight (kg)
Safety – Physical Examination	Physical Examination – Investigator Reported Body Surface Area (m ²)
Safety – Physical Examination	Physical Examination – Calculated Body Surface Area (m ²)
Safety	Exposure to Subsequent Surgery

11.2 Planned Figures

Category	Graph Title
Effectiveness	Kaplan-Meier Plot of Progression-free Survival Time
Effectiveness	Kaplan-Meier Plot of Overall Survival Time

12. APPENDICES

12.1 Handling of Dates, Incomplete Dates and Missing Dates

Dates for the following variables will be imputed using the algorithm described below:

- Adverse events
- Concomitant medications

Imputation rules for partial or missing AE/concomitant medication start dates:

Start Date		Stop Date						
		Complete: yyyymmdd		Partial: yyyy-mm		Partial: yyyy		Missing
		< 1 st dose	≥ 1 st dose	< 1 st dose yyyy-mm	≥ 1 st dose yyyy-mm	< 1 st dose yyyy	≥ 1 st dose yyyy	
Partial: yyyy-mm	= 1 st dose yyyy-mm	2	1	2	1	n/a	1	1
	≠ 1 st dose yyyy-mm		2		2	2	2	2
Partial: yyyy	= 1 st dose yyyy	3	1	3	1	n/a	1	1
	≠ 1 st dose yyyy		3		3	3	3	3
Missing		4	1	4	1	4	1	1

1 = Impute the date of first dose

2 = Impute the first of the month

3 = Impute January 1 of the year

4 = Impute January 1 of the stop year

Note: If the start date imputation leads to a start date that is after the stop date, then do not impute the start date.

Imputation rules for partial or missing AE/concomitant medication stop dates:

1. Initial imputation
 - a. For partial stop date mm-yyyy, impute the last of the month.
 - b. For partial stop date yyyy, impute December 31 of the year.
 - c. For completely missing stop date, do not impute.
2. If the stop date imputation leads to a stop date that is after the death date, then impute the stop date as the death date.

3. If the stop date imputation leads to a stop date that is before the start date, then there is a data error and do not impute the stop date. (ie. set the stop date as missing).

- Deaths

Imputation rules for partial or missing *death dates*:

1. If death year and month are available but day is missing:
 - If mmYYYY for last contact date = mmYYYY for death date, set death date to the day after the last contact date.
 - If mmYYYY for last contact date < mmYYYY for death date, set death date to the first day of the death month.
 - If mmYYYY for last contact date > mmYYYY for death date, data error and do not impute.
2. If both month and day are missing for death date or a death date is totally missing, do not impute.

Imputation rules for partial or missing *stop dates for prior radiotherapy*:

1. Initial imputation
 - a. For partial stop date mmYYYY, impute the last of the month.
 - b. For partial stop date yyyy, impute December 31 of the year.
 - c. For completely missing stop date, do not impute. Raise date issue to Statistician.
2. If the stop date imputation leads to a stop date that is on or after the first dose date of trabectedin administration, then impute the stop date as the day prior Day 1.

Imputation rules for partial or missing *start cycle dates of prior chemo*:

Start Date	Stop Date
------------	-----------

		Complete: yyyymmdd		Partial: yyyyymm		Partial: yyyy		Missing
		< 1 st dose	≥ 1 st dose	< 1 st dose yyyyymm	≥ 1 st dose yyyyymm	< 1 st dose yyyy	≥ 1 st dose yyyy	
Partial: yyyyymm	= 1 st dose yyyyymm	2	2	2	2	n/a	2	2
	≠ 1 st dose yyyyymm		2		2	2	2	2
Partial: yyyy	= 1 st dose yyyy	3	3	3	3	n/a	3	3
	≠ 1 st dose yyyy		3		3	3	3	3
Missing		4	4	4	1	4	1	5

1 = Impute the date of first dose

2 = Impute the first of the month

3 = Impute January 1 of the year

4 = Impute January 1 of the stop year

5 = do not impute

Note: If the start date imputation leads to a start date that is after the stop date, then do not impute the start date.

Imputation rules for partial or missing *prior chemo date of last cycle*:

1. Initial imputation
 - a. For partial stop date mmYYYY, impute the last of the month.
 - b. For partial stop date YYYY, impute December 31 of the year.
 - c. For completely missing stop date, do not impute.
2. If the stop date imputation leads to a stop date that is after the death date or after first dose date of trabectedin, then impute the stop date as the death date or first dose date of trabectedin whichever is earlier.
3. If the stop date imputation leads to a stop date that is before the start date, then there is a data error and do not impute the stop date. (ie. set the stop date as missing) and inform the Statistician.

Imputation rules for partial or missing *prior surgery and prior radiotherapy dates*:

Apply imputations, if needed,

- a. For partial date mm/yyyy, impute the first of the month.
- b. For partial date yyyy, impute Jan 1st of the year.
- c. For completely missing, do not impute.

Exclude from table any data with imputed date of medical history or surgery with a year after first dose date year and inform Statistician of any data in medical history or surgery with a date reported after first dose date.

Imputation rules for partial or missing *medical history dates*:

If year of diagnosis is missing impute with year of day 1 of trabectedin.

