4.3.1 Selection Criteria

Patients must comply with all of the following criteria in order to be enrolled into the study:

- Patients must be aged 18 years or older.
- Patients must have platinum-sensitive relapsed ovarian cancer, defined as disease relapse that occurs 6 months or more after completion of last platinum-containing therapy.
- Treatment indication according to local label SmPC and reimbursement for trabectedin and PLD treatment.
- Patients must have received a minimum of 1 cycle of trabectedin + PLD before their inclusion in the study.
- Patients must have signed an informed consent document indicating that they understand the
 purpose and procedures required for the study and are willing to participate in the study.

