9.3 Demographic and Baseline Characteristics

Summary statistics for each of the following demographic and baseline characteristics will be tabulated based on the FAS:

- Age as continuous and categorical : <65, [65, 75) and ≥ 75 years
- ECOG/WHO performance status
- BRCA-1/2 status
- Baseline weight, height, investigator reported BSA and derived BSA
- Time since initial ovarian cancer diagnosis, tumor grade and histology at initial tumor diagnosis
- Time since relapsed ovarian cancer diagnosis
- Prior tumor therapies, including surgery, and radiotherapy
- Occurrence of physical examination abnormalities and body systems in which abnormalities were found

- Anti-tumor treatment (chemo and non-chemo) including bevacizumab usage, PD reported during or after bevacizumab, number of regimens received, best response reported for the latest regimen received prior to trabectedin, time since latest regimen last dose taken, time since latest regimen reported PD and recurrence
- Medical history: co-morbidities
- Baseline imaging

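### SAP 12.1 can date a prior chemotherapy regimen entirely to the first trabectedin dose, giving it zero length and a zero interval before study treatment in the baseline tables

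*SAP*

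**What the plan says.** SAP 8.2 sends incomplete dates for prior anticancer therapies to the algorithms in SAP 12.1. Three rules there matter.

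- **Start of prior chemotherapy.** When the start is wholly missing, the code depends on the stop date. If the stop is known only to the month or year, and falls in or after the month or year of the first trabectedin dose, the code is "1 = Impute the date of first dose". A complete stop date, or a partial one before the first-dose month or year, takes "4 = Impute January 1 of the stop year". If the stop is missing too, nothing is imputed (code 5). A note cancels the imputed start only if it falls after the stop.
- **Last cycle of prior chemotherapy.** A year-only date becomes 31 December. If that is later than the first trabectedin dose or death, it is reset to the earlier of the two.
- **Medical history.** Under "medical history dates" the SAP says "If year of diagnosis is missing impute with year of day 1 of trabectedin".

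SAP 9.3 lists the outputs that could use these dates. They include "time since latest regimen last dose taken", best response to the latest regimen, and "Time since initial ovarian cancer diagnosis, tumor grade and histology at initial tumor diagnosis". Protocol 4.3.1 defines platinum-sensitive disease as "disease relapse that occurs 6 months or more after completion of last platinum-containing therapy".

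**The concern.** A regimen given before trabectedin cannot begin on the day trabectedin begins. Dating an event of unknown start to first dose is cautious for adverse events, because it counts the event as treatment-emergent. It has no such purpose for prior therapy.

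The interval since the last regimen is a main descriptor of a relapsed platinum-sensitive population, and it will be shown by prior antiangiogenic use beside PFS. Artificial zeros make some patients look as if they went straight from one regimen to the next, which for platinum would mean that they were not eligible.

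**Working it through.** The documents give no figure to reproduce here, so the check traces the rules and does the date arithmetic.

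**1. Where code 1 comes from.** The adverse-event start-date table has 12 cells with code 1: four in the row for a partial month equal to the first-dose month, four in the row for a partial year equal to the first-dose year, and four in the missing-start row. The prior-chemotherapy table has the same layout. Ten of the 12 cells now carry code 2, 3, 4 or 5, and two still carry code 1. The missing-start row reads 4, 4, 4, 1, 4, 1, 5. No reason is given for using code 1 in two partial-stop cells when a complete stop on or after first dose takes code 4.

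**2. Which cell is realistic.** For a platinum regimen, a stop in the first-dose month would itself breach the entry rule. The month-only cell is therefore reached only by non-platinum regimens or data errors. The year-only cell can hold a genuine platinum regimen that ended earlier in the same year. With first-dose dates spread evenly over a 365-day year (assumed) and 6 months taken as 183 days, this is possible for (365 − 183)/365 = 49.9% of first-dose dates.

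**3. Worked example.** First dose 15 October 2017 (illustrative), start missing.

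| Stop recorded as | Stop used | Start used | Length | Days from stop to first dose |
|---|---|---|---|---|
| 2017-03 | 31 Mar 2017 | 1 Jan 2017 (code 4) | 89 | 198 |
| 2017 | 31 Dec 2017, capped to 15 Oct 2017 | 15 Oct 2017 (code 1) | 0 | 0 |

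In the second line the start equals the capped stop, and it precedes the uncapped stop. On either comparison the start is not after the stop, so the safeguard does not act. Losing only the month of the stop moves the start 287 days later (1 January to 15 October) and reduces the interval from 198 days to 0.

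**4. Size for one patient.** If this was her last platinum regimen, the entry rule puts completion no later than about 15 April 2017, and the recorded year puts it no earlier than 1 January 2017. The true interval is therefore 183 to 287 days, or 6.0 to 9.4 months at 30.4375 days per month. The table would use 0.

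**5. Size for the summary.** Shift in mean interval = share affected × true interval. The share is not in the documents, so I assume 1% to 20%.

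- 1% (3 of 300 patients): 0.01 × 6.0 to 9.4 = 0.06 to 0.09 months.
- 5% (15 of 300): 0.30 to 0.47 months.
- 20% (60 of 300): 1.2 to 1.9 months.

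The minimum is a planned statistic (SAP 9.1), and one such record is enough to make it 0.

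**6. Which rule feeds which output.** No latest-regimen item in SAP 9.3 is stated to use a start date. The interval since last dose comes from the last-cycle date, so the cap produces the zero. The cap also puts the regimen last if regimens are ordered by stop date. Code 1 does the same if they are ordered by start date. Correcting code 1 alone would leave the interval at zero.

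**7. Year of diagnosis.** SAP 9.3 has "Medical history: co-morbidities" as its own item, apart from time since cancer diagnosis. Footnote 2 to Protocol Table 1, however, includes key features of the disease in medical history. The exclusion check in SAP 12.1 removes only years after the first-dose year, so it would not catch an imputed year equal to that year.

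**The case against.** The strongest reply is that little depends on this. Code 1 occupies two of seven missing-start cells, one of which is hardly reachable, and no listed output clearly uses a start date. PFS, OS and response in SAP 5.3 use none of these dates. All of that stands, and it limits the point to the baseline description. It does not remove the point, because the year-only stop is a plausible record and the cap feeds a listed output directly.

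Two stronger readings are tempting, and the documents do not support them.

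- A reader might infer that the diagnosis rule gives the ovarian cancer an impossible date. The heading and SAP 9.3 point to co-morbidities, and SAP 8.2 does not list diagnosis among the imputed dates. The rule also fills a calendar year, not a date. Even applied to the cancer, a same-year diagnosis is not always excluded. If platinum treatment took D months (assumed), it remains feasible for 49.9% of first-dose dates at D = 0 and 8.2% at D = 5. A downward shift in mean time since diagnosis can be calculated, for example 0.05 × (24 − 6) = 0.9 to 0.10 × (48 − 6) = 4.2 months. The missing share, the true mean and the 1 January fill behind it are all assumed, and so is the scope.
- A reader might infer that patients would be put in the wrong antiangiogenic group. SAP 9.1 groups by previous use, yes or no. No filter on a regimen's start relative to Day 1 is stated, so nothing shows that the imputed start affects grouping.

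**Conclusion.** The point holds for prior chemotherapy. Two cells of the start-date table appear to be left over from the adverse-event table. Together with the last-cycle cap they can place a whole prior regimen on Day 1. In the worked platinum case, an interval that must be at least 6 months is reported as 0.

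The effect is confined to descriptive baseline tables and probably to few records. At an assumed 5% of patients, all like the worked example, the mean interval falls by 0.3 to 0.5 months and the minimum becomes 0. The number of year-only stop dates is unknown. The entry-rule contradiction applies to platinum-containing regimens only.

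The year-of-diagnosis rule needs only a sentence on scope. As written it is unclear, but it has not been shown to be wrong.

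**What to change.** In SAP 12.1:

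- In the missing-start row for prior chemotherapy, replace both code-1 cells with code 5 (do not impute).
- When the imputed last-cycle date would be set only by the first-dose cap, treat it as missing for the interval summary.
- Choose the latest regimen by the recorded line of therapy, which Protocol 6.2.1 collects, not by imputed dates.
- State that the year-of-diagnosis rule covers co-morbidities only, and that a missing year of ovarian cancer diagnosis is not imputed.
- Report the number missing for each affected item, overall and by prior antiangiogenic use.

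The cost is a few lines of SAP text and a small program edit. A few patients will be shown as missing. Those left out of the interval summary stopped their last regimen in the year trabectedin began, so they tend to have shorter intervals and the remaining mean may be slightly high. Reporting the count lets a reader judge this. SAP 12.1 already leaves wholly missing prior-surgery dates, and prior chemotherapy with both dates missing, unimputed.

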12.2 Handling of Missing Total Dose Received

In the event of total dose data reported as unknown for a cycle prior to IC, of either trabectedin or PLD, then imputation of total dose will be performed. If the total dose is missing the value will be imputed using last observation carried forward (LOCF) and last observation carried backwards (LOCB) as necessary.
